### 16. Consent and Withdrawal

Participants may withdraw from the study at any time without affecting their standard medical care. Any samples collected from the participant may be destroyed upon request. However, de-identified data already entered the database cannot be deleted, nor can data already downloaded by authorized researchers be retrieved. Withdrawal from the study will not in any way affect the participant's access to medical care, and they will continue to receive healthcare services from our hospital.

### 17. Adverse Events (AEs)

#### 1. Severity Levels

The severity of adverse events (AEs) will be graded on a scale of 1 to 5.

#### 2. Collection and Reporting

The collection of AEs, including serious adverse events (SAEs), will begin from the first administration of FMT. Routine AE collection will continue until week 1. Since participants will transition to standard care after week 1, AEs occurring beyond this period will not be collected.

#### Anticipated Clinical Events Following FMT

FMT is known to be associated with certain characteristic signs and symptoms (listed below). These

symptoms are typically mild and resolve within three days post-FMT. Unless symptoms persist for more than three days or become more severe, they will not be recorded as AEs.

- |                                |                        |                        |
|--------------------------------|------------------------|------------------------|
| ▪ Sore throat                  | ▪ Abdominal distention | ▪ Vomiting             |
| ▪ Fever                        | ▪ Abdominal pain       | ▪ Excessive flatulence |
| ▪ Increase of CRP              | ▪ Abdominal fullness   | ▪ Constipation         |
| ▪ Diarrhea                     | ▪ Bloating             | ▪ Decreased appetite   |
| ▪ Increased in stool frequency | ▪ Belching             | ▪ Headache             |
| ▪ Loose stool                  | ▪ Cramping             | ▪ Nausea               |
| ▪ Abdominal discomfort         | ▪ Gassiness            | ▪ Borborygmus -----    |
|                                | ▪ Fatigue              |                        |

UC is associated with certain characteristic signs and symptoms, including diarrhea, rectal bleeding, and abdominal pain. These signs and symptoms may be present at baseline and can persist or fluctuate throughout the study based on the subject's medical history. These signs and symptoms will not be collected as AEs. However, an exacerbation of disease activity (e.g., an increase in daily rectal bleeding or abdominal pain beyond the subject's normal fluctuations, or the emergence of new signs and symptoms of UC) will be collected as AEs and reported in accordance with regulatory requirements. Extraintestinal manifestations of UC (e.g., joint pain, arthritis, uveitis) that develop or worsen during the study will also be considered AEs.

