Our team's high-quality research findings indicate that the gut microbiota of populations in Yunnan's ethnic minority regions exhibits significantly higher diversity and regional specificity compared to urban populations. This has potential value in enhancing FMT efficacy. Previous studies [12] revealed ethnic and regional differences in IBD prevalence in Yunnan Province, with lower rates among the Dai, Bai, and Miao ethnic groups compared to the Han population. An analysis of contributing factors highlighted the protective role of traditional ethnic diets, which increase gut microbial and viral diversity and probiotics content, thereby reducing UC prevalence. Based on this, the differences between donors in FMT may affect treatment outcomes, emphasizing the importance of identifying "high-quality" donors who maximize efficacy and minimize adverse reactions.

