### 1.FMT:

Fresh fecal bacterial solution was obtained through the fecal bacterial transplantation isolation system (FMT-6A-50/12-AS, Nanjing), which was directly infused into the ileocecal region through the TET tube of colonoscopy within 30 minutes, 100 mL each time. The fresh fecal bacterial solution was given at an interval of one day for a total of 3 transplantations.

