#### 12. Potential Risks

There is a potential risk of perforation during colonoscopy, but the overall incidence of

complications is less than 1%. The risk of infectious diseases during fecal microbiota transplantation (FMT) is minimal due to rigorous donor screening prior to transplantation. To date, FMT appears to be safe. Over 200 FMT procedures have been conducted at the Academic Medical Center in Amsterdam and more than 3,000 at the Digestive Disease Center in Sydney, Australia, without any reports of serious adverse events. Mild adverse reactions such as bloating, flatulence, borborygmi, vomiting, and abdominal discomfort may occasionally occur. Only qualified researchers have access to de-identified data in the database. Furthermore, they agree not to use this information to attempt to identify the data providers, ensuring participant confidentiality. However, given the availability of current public-domain technologies and expected advancements in the coming years, identifying specific individuals from genetic or other information may become feasible and increasingly straightforward. Participants and their family members may face potential risks (e.g., those related to insurance, employment, cybersecurity breaches, and law enforcement) due to shared genetic characteristics.

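### The three-day rule for expected post-FMT symptoms leaves typical acute reactions out of the AE record, so the safety summary would say little about them by donor

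*Combined protocol and SAP*

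**What the plan says.** Section 17, Anticipated Clinical Events Following FMT, lists symptoms known to follow FMT and says that these "symptoms are typically mild and resolve within three days post-FMT". It then sets the recording rule: "Unless symptoms persist for more than three days or become more severe, they will not be recorded as AEs". The next paragraph of that section treats UC symptoms separately. Background UC symptoms are not collected, but the text continues: "However, an exacerbation of disease activity (e.g., an increase in daily rectal bleeding or abdominal pain beyond the subject's normal fluctuations". Such exacerbations, newly emerging UC signs, and new or worsening extraintestinal manifestations are AEs.

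Other parts of the protocol bear on the rule:

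- Section 1 (Background) describes the donors sought as "donors who maximize efficacy and minimize adverse reactions".
- Section 5, FMT: "The fresh fecal bacterial solution was given at an interval of one day for a total of 3 transplantations". The schedule table places the infusions in the week 1 column.
- Section 12 (Potential Risks): "Mild adverse reactions such as bloating, flatulence, borborygmi, vomiting, and abdominal discomfort may occasionally occur".
- Section 17, Collection and Reporting: "Routine AE collection will continue until week 1". The schedule table, by contrast, marks AEs at weeks 1, 8 and 12.
- Section 17, Severity Levels, provides a grade from 1 to 5.
- Section 11 plans a descriptive summary of safety data.

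**The concern.** The recording threshold is the same three days in which the protocol expects the reaction to end. The rule therefore removes the typical case and keeps the atypical one. The protocol describes no other instrument, such as a symptom diary or solicited-reaction form, from which the missing events could be recovered later.

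The trial compares two donor sources, and its Background names few adverse reactions as one mark of a good donor. Short-lived reactions to the infusions are one natural tolerability contrast. Under the rule as written they would not reach the section 11 summary, whichever donor was used.

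Two ambiguities add to this. Becoming more severe is not tied to any starting point or to the 1-to-5 grade. A brief week-1 episode of diarrhea or abdominal pain could fall under the FMT list or under UC exacerbation, and no precedence is given. Section 5 says that all investigators know the allocation, so how these judgements are made could differ between arms.

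**Working it through.** The protocol states no reaction rate and no safety calculation, so there is no figure of its own to reproduce. The check is a reading of the rule, followed by day arithmetic.

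**1. Size of the list.** The three columns in section 17 hold 7 + 8 + 7 = 22 items.

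**2. Threshold against expected duration.** Expected course: resolved within three days. Recorded only if: longer than three days, or more severe. The two duration conditions do not overlap. A listed symptom that behaves as the protocol expects, and does not worsen, is never recorded as an AE.

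**3. Comparison with section 12.** The five mild adverse reactions named there are bloating, flatulence, borborygmi, vomiting and abdominal discomfort. Each appears in the section 17 list, so 5 of 5 fall under the rule.

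**4. What is still captured.** SAEs from the first FMT (section 17, Collection and Reporting); listed symptoms that persist or worsen; events not on the list; UC exacerbations; extraintestinal manifestations; and CRP as a laboratory test (section 5, Clinical Laboratory Tests), which the schedule table appears to mark at screening, week 1 and week 8. A CRP rise that comes and goes between draws would be missed.

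**5. Timing of the third infusion.** Take week 1 to end on day 7 (assumed). A symptom starting with an infusion on day t passes the duration threshold only after day t + 3, so the days left for recording are 7 − (t + 3). The infusion interval can be read in more than one way, so the infusion days below are assumptions.

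| Infusion days | Third infusion | Threshold passed after | Days left |
|---|---|---|---|
| 0, 2, 4 | day 4 | 4 + 3 = day 7 | 7 − 7 = 0 |
| 1, 3, 5 | day 5 | 5 + 3 = day 8 | 7 − 8 = −1 |
| 0, 1, 2 | day 2 | 2 + 3 = day 5 | 7 − 5 = 2 |

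On either alternate-day schedule, a reaction to the third infusion can hardly qualify by duration before collection stops. On consecutive days about two days remain. For a first infusion on day 0, four days remain (7 − 3), so the difficulty lies mainly with the last infusion. All of this uses the week-1 cut-off in section 17. If the schedule table's weeks 8 and 12 applied, the cut-off would not bind.

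**6. Illustration of the loss (assumed rates).** With 50 per arm (section 10), a true rate p of listed reactions and a fraction r of affected patients who meet the rule, the expected recorded cases are 50 × p × r. Take p = 30% and 60%, so the true counts are 15 and 30:

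- r = 5%: 0.75 v 1.5
- r = 10%: 1.5 v 3
- r = 20%: 3 v 6
- r = 50%: 7.5 v 15

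The documents supply neither p nor r. The list shows only that the result depends on r, and that a true gap of 15 patients would appear as a gap of between 0.75 and 7.5 over this range.

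**The case against.** The strongest reply is that much safety information survives (step 4), that the rule is the same in both arms, and that this is a pilot. Minimizing adverse reactions appears only in the Background. The objectives in section 2 name efficacy, section 3 lists no safety outcome, and section 11 plans no formal safety test. All of that stands. A reader might infer that the donor safety comparison is empty, or that a planned test is voided. The documents support neither.

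A reader might also add up three-day windows after each infusion and conclude that the whole of week 1 is exempt. That misreads the rule, which filters on how long a symptom lasts and not on calendar days. Diarrhea from day 0 to day 5 lasts more than three days and is recorded. Reactions that run together across infusions are more likely to qualify.

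Nor is the overlap with UC exacerbation a flat contradiction. Both paragraphs bring in symptoms that worsen, so they largely agree there. What remains is an ambiguity about brief new episodes.

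Differential recording between arms is a possibility and not a finding. No section says who classifies AEs, and section 7 says both that investigators know the donor and that access to donor identity is limited to preparation staff. The documents also do not say that short reactions are where donors differ, or that early fever or raised CRP signals infection from a donor.

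None of this answers the main point: the expected reaction is filtered out and nothing else is described that records it.

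**Conclusion.** The point holds in a limited form. As written, the rule drops the typical acute reaction for 22 listed signs and symptoms, including every mild reaction that section 12 names. The section 11 summary would then be largely uninformative about expected acute reactions by donor, although it would still carry information on more serious, prolonged, worsened and unlisted events. The primary outcome is not affected.

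The number of events lost cannot be stated, because the protocol gives no rates. The third-infusion difficulty assumes alternate-day infusions and the section 17 cut-off at week 1; it is milder with consecutive-day infusions. The conflict between that cut-off and the schedule table is a separate matter, but the two passages need to be reconciled before the timing can be settled. The change is worth making because it is cheap and because these data cannot be recovered once the trial has run.

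**What to change.** Replace the sentence in section 17 that keeps listed symptoms out of the AE record. In its place:

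- At the infusion visits and the week-1 contact, record each listed symptom with onset date, stop date and the 1-to-5 grade already in section 17. Flag it as expected.
- Tabulate these events by donor arm in the section 11 safety summary.
- Define more severe as an increase in that grade, and record the starting grade so that the reference point is explicit.
- State that no persistence or severity filter ever applies to SAEs.
- State that a symptom that could be either an FMT reaction or a UC exacerbation is always recorded.

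Symptoms need not be attributed to a particular infusion, which closely spaced infusions would make unreliable.

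The cost is a symptom checklist at contacts already planned, with no extra procedure. The downsides are more low-grade entries, some recall error in dates collected at the week-1 contact, and an AE table that looks less favourable.
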